NKTR-118 was well-tolerated in the Phase II study at 5 and 25 mg/day with the most commonly reported side effects being GI in nature (abdominal pain, diarrhea, and nausea) and most frequent in the 50 mg cohort. The frequency of any GI AE was 53% in the 25 mg/day dose group and 48% in the corresponding placebo group. In the 50 mg/day dose group, the GI AE frequency was 69% and 27% in the corresponding placebo group. In the 5 mg/day dose group, the frequency was 46% and 34% in the corresponding placebo group. Most of the AEs were rated mild or moderate. During the double-blind phase, a total of 12 patients discontinued the treatment permanently due to AEs (10 patients in the 50 mg dose group, 1 patient in the 25 mg/day dose group, and 1 patient in the 5 mg/day dose group). Most of the discontinuations were due to GI AEs. There was 1 serious adverse event (SAE) of upper abdominal pain in the 50 mg dose cohort, which was considered to be related to the study drug by the investigator. The patient was briefly monitored in a hospital setting due to this event, which resolved spontaneously without medical sequelae. No reversal of analgesia was seen at any dose in Phase II, as measured by changes in the daily opioid dose or by Numerical Rating Scale (NRS) for pain. A significant increase in total Clinical Opioid Withdrawal Scale (COWS) score for the NKTR-118 50 mg group was noted as compared with placebo at Day 1 of the double-blind treatment period. When the GI component of the COWS instrument (eg, diarrhea, abdominal cramps) was removed from calculation of total COWS scores, there was no longer a significant difference, indicating a lack of increase in the components of the scale that reflect CNS withdrawal. Although these data suggest that the risk for reversal of analgesia or precipitation of opioid withdrawal is unlikely, it is recommended that investigators remain vigilant regarding this potential effect of NKTR-118.

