- Care should be taken to record heart rate and blood pressure, which at this visit should be performed 1 hour post-dose/after initial assessments. (For practical purposes, this can be performed and recorded within a window from 1 hour to 90 minutes post-dose/initial assessments).

Please see Section [6.3.12.1](#) for additional details on the protocol-mandated methods for collection of vital signs. The accurate time in date, hours, and minutes will be recorded for this measurement.

Additionally, if clinically significant decreases in blood pressure are noted at this post-dose/additional vital signs measurement, an additional measurement should be

taken approximately 2 hours later prior to the patient leaving the clinic (please refer to Section 6.3.12.1 for guidelines on management.)

In the event of clinically significant findings compared to the pre-dose/initial measurements (per the judgment of the investigator or delegate) please refer to Sections 5.8 and 6.3.13.3.

- Triplicate 12-lead ECGs will be obtained 2 hours after the dose of study drug (NKTR-118 patients) or 2 hours after initial assessments are completed (Usual Care patients).
- Modified Himmelsbach scale will be completed by the investigator 2 hours after the patient receives the dose of study drug (NKTR-118 patients) or 2 hours after initial assessments are completed (Usual Care patients).
- Study drug will be dispensed and dosing instructions will be provided (NKTR-118 patients only).
- A new supply of bisacodyl will be dispensed (NKTR-118 patients only).
- Patients will be given a home diary to record their use of breakthrough pain opioid medication and other concomitant medications between visits.
- An appointment for Visit R2 (Week 1) will be made. NKTR-118 patients will be instructed to bring study drug and unused bisacodyl with them to the visit.

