- ^g For new patients, determined based on self reported laxative use over the 2 weeks prior to the screening visit, continued constipation symptoms, and laxative side effects. For patients entering from other NKTR-118 studies, laxative response status will be transcribed from the relevant pivotal efficacy and safety study.
- ^h Urine pregnancy tests will be performed at screening (new patients only), randomization (Visit R1), and M12. Any positive urine pregnancy test is to be followed up with a serum pregnancy test. Serum pregnancy tests will be performed at M1, M3, M6, M9, and the follow-up visit.
- ⁱ A single 12-lead ECG will be obtained for new patients at Screening (Visit S1), and for all patients at the follow-up visit. Triplicate ECGs will be performed for all patients at randomization (Visit R1, pre-dose and 2 hours post-dose) and at all other study visits.
- ^j Laboratory tests for new patients can be repeated once after consultation with the sponsor if assessment at screening is abnormal and clinically significant as judged by the investigator. Results (including repeat laboratory testing) must be reviewed prior to randomization to ensure patient meets eligibility requirements.
- ^k If U/A is positive for blood, protein, or glucose, microscopic testing is to be conducted.
- ^l If, in the opinion of the investigator, a patient is undergoing opiate withdrawal or significant exacerbation of pain, the investigator is to conduct a repeat urine drug screen to rule out noncompliance with the opioid regimen as an explanation for withdrawal or pain. In addition, the investigator may perform a urine drug screen anytime during the study, at his/her discretion, to allow appropriate medical management of the patient.
- ^m Completed before the first dose for all patients and 2 hours after the first dose for patients randomized to NKTR-118 during Visit R1.
- ⁿ For new patients, prior medications will be collected from 60 days before screening; for patients enrolling from other studies prior medications will be collected from 60 days before randomization.

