6.3.1 Safety variables

Safety variables include:

- Incidence, nature, and intensity of AEs, treatment-related AEs, SAEs, AEs leading to discontinuation, and specific safety areas of interest
- Mean daily opioid dose for Months 1, 3, 6, 9, and 12
- Mean bisacodyl dose per week for Months 1, 3, 6, 9, and 12 (NKTR-118 group only)
- Change from baseline in NRS pain score for Week 1, Week 2, Months 1, 2, 3, 6, 9, and 12.
- Observed values and change from baseline in composite score in modified Himmelsbach scale for the evaluation of centrally mediated opioid withdrawal symptoms for Week 1, Months 1, 3, 6, 9, and 12
- Changes in vital signs and physical examination
- Changes in laboratory assessments (ie, chemistry, hematology, and U/A)
- Changes in ECGs

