11.1.5 Modified Himmelsbach Scale

The scores for each of 8 signs are summed to give a composite score ranging from 0 to 24 for each visit, where higher values indicate greater severity of symptoms. If more than 25% of the 8 signs are missing at a visit, the composite score will be set to missing. The composite score will be summarized at Week 1, Months 1, 3, 6, 9, and 12. Changes from baseline to Week 1, Months 1, 3, 6, 9, and 12 in the modified Himmelsbach scale will be calculated as the post-baseline value minus the baseline value. Negative changes from baseline indicate improvement.

For the new patients, baseline modified Himmelsbach values will be defined as the latest non-missing value collected prior to the first dose of study drug in this study (screening, Visit S1 or Week 0, Visit R1). For patients entering the study from a previous NKTR-118 study (D3820C00005 or D3820C00007), the primary baseline modified Himmelsbach values will be defined as the latest non-missing value collected prior to the first dose of study drug in the previous pivotal study (D3820C00004 or D3820C00005) (screening, Visit 1 or Week 0, Visit 3), and supportive baseline modified Himmelsbach will be defined as the data collected at the final visit from the previous study.

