11.1.11 Vital signs

Changes from baseline in vital signs (sitting blood pressure and pulse) at each post-baseline visit (Week 0 [1 hour post-dose], Week 1, Week 2, Months 1, 3, 6, 9, 12, and 2 week follow-up) will be derived as the post-baseline value minus the baseline value for the same assessment. Markedly abnormal values or changes from baseline will be identified.

For the new patients, baseline vital sign values will be defined as the latest non-missing value collected prior to the first dose of study drug in this study (screening, Visit S1 or Week 0, Visit R1 [pre-dose]). For patients entering the study from a previous NKTR-118 study (D3820C00005 or D3820C00007), the primary baseline vital sign values will be defined as the latest non-missing value collected prior to the first dose of study drug in the previous pivotal study (D3820C00004 or D3820C00005) (screening, Visit 1 or Week 0, Visit 3), and supportive baseline vital sign values will be defined as the data collected at the final visit from the previous study.

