12.2.1 Safety analyses

Adverse events will be coded using the MedDRA dictionary. Three sets of AE summaries will be generated: (1) all AEs recorded in the clinical database, (2) all TEAEs (as defined in Section 11.1.1), and (3) AEs occurring after the last dose of study drug.

Number of events and proportions will be tabulated by preferred term and system organ class. An event that occurred 1 or more times on the date of or subsequent to first dose of study drug will contribute 1 observation to the numerator of the proportion. The denominator of the proportion will comprise all patients in the Safety analysis set. Adverse events will also be

summarized by intensity and separately, by causality (as determined by the investigator). Should a patient experience the same preferred term/system organ class within multiple intensity or causality categories, the patient's worst occurrence (most severe/most related) will be retained in the tabulations. Serious AEs and commonly occurring AEs will be summarized in a generally similar manner. Adverse events of special interest may be further summarized and analysis of AEs occurring within specific time periods (e.g. after 3 months, after 6 months, etc.) may be considered.

Adverse events, SAEs, AEs leading to death, and AEs leading to study discontinuation will be tabulated for each treatment group. Descriptive statistics for time to onset and duration of select AEs may be summarized by treatment group. Adverse events that could potentially be indicative of centrally mediated opioid withdrawal, abuse potential, and bowel perforation will be identified prior to database lock and will also be summarized by each treatment group.

The mean daily opioid dose will be summarized for the following intervals: randomization to Month 1, Months 1 to 3, Months 3 to 6, Months 6 to 9, and Months 9 to 12. The mean bisacodyl dose per week will be summarized only for the NKTR-118 treatment group using descriptive statistics for the following intervals: randomization to Month 1, Months 1 to 3, Months 3 to 6, Months 6 to 9, and Months 9 to 12. The observed composite modified Himmelsbach score and change from baseline will be summarized by treatment group at Week 1, Months 1, 3, 6, 9, and 12 using descriptive statistics. The observed score and change from baseline in the NRS pain scores (average in the 7 days prior to the study visit) will be summarized by treatment group for Weeks 1 and 2, Months 1, 2, 3, 6, 9, and 12.

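### The 2-hour first-dose withdrawal score is missing from all three lists of modified Himmelsbach summary time points, its collection in Usual Care is contradicted by Table 1, and Week 0 changes in rollover patients use a pre-pivotal-study value as primary baseline

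*Protocol*

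**What the plan says.** **Collection.** Section 3.1.2.1 (Visit R1, post-dose assessments) says: "Modified Himmelsbach scale will be completed by the investigator 2 hours after the patient receives the dose of study drug". The same bullet sets the Usual Care score 2 hours after initial assessments, and the section states elsewhere that Usual Care patients have the same observations as the NKTR-118 group. Table 1 footnote m reads differently: "Completed before the first dose for all patients and 2 hours after the first dose for patients randomized to NKTR-118 during Visit R1".

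**Analysis of the scale.** Three sections fix the time points. Section 6.3.1 defines the variable "for the evaluation of centrally mediated opioid withdrawal symptoms for Week 1, Months 1, 3, 6, 9, and 12". Section 11.1.5 says "The composite score will be summarized at Week 1, Months 1, 3, 6, 9, and 12" and gives changes from baseline at the same visits. Section 12.2.1 says: "composite modified Himmelsbach score and change from baseline will be summarized by treatment group at Week 1, Months 1, 3, 6, 9, and 12".

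**Analysis of ECG and vital signs.** Section 11.1.10 lists Week 0 at 2 hours post-dose, and Section 11.1.11 lists Week 0 at 1 hour post-dose, each as a post-baseline time point.

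**Baselines.** For rollover patients, Section 11.1.11 ties the reference to the earlier pivotal trial, not to this one: "primary baseline vital sign values will be defined as the latest non-missing value collected prior to the first dose of study drug". The same sentence makes the final visit of the previous study the supportive baseline. Section 11.1.10 does the same for ECG and Section 11.1.5 for the withdrawal scale. Section 12.2 plans rollover change summaries with both baselines, where appropriate.

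**The concern.** Opioid withdrawal is the first safety topic of interest in Section 6.3.14, and Section 3.2 gives assessment of withdrawal as the reason for including the scale. The 2-hour score is the only one taken on the day of the first dose after that dose. As the lists stand, the summaries of the scale begin a week later.

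The conflict over footnote m concerns collection. Scores not taken in Usual Care patients at R1 cannot be recovered, and the secondary objective is a descriptive comparison with that arm.

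The baseline rule raises a smaller, related point. Cardiovascular events, including blood pressure and heart rate abnormalities, are also named in Section 6.3.14. A reading 1 or 2 hours after dosing is meant to show an acute effect, and Section 3.1.2.1 itself judges the post-dose blood pressure against the pre-dose one. The primary change in rollover patients uses a different and much older reference.

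**Working it through.** No sample-size, power or error-rate figure is involved. The check sets the collection schedule beside the analysis lists.

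**1. Assessments after the first dose.**

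| Modified Himmelsbach assessment | Collected (3.1.2.1 to 3.1.2.9, Table 1) | In 6.3.1, 11.1.5 and 12.2.1 |
|---|---|---|
| R1, 2 hours | yes | no |
| Week 1 | yes | yes |
| Months 1, 3, 6, 9, 12 | yes | yes |

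Collected: 1 + 1 + 5 = 7. Listed: 1 + 5 = 6. The one left out is R1 at 2 hours. The omission looks unintended, because the ECG and vital-sign sections name their Week 0 post-dose reading.

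**2. Who is scored at 2 hours.** About 1135 patients are planned at 2:1, so 1135 × 2/3 ≈ 757 on NKTR-118 and 1135 × 1/3 ≈ 378 on Usual Care. Under Section 3.1.2.1 both groups are due a 2-hour score. Under footnote m only the first is, leaving 0 of about 378 comparator scores. These are planned numbers, not observed ones.

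**3. Age of the rollover baseline at the Week 0 post-dose reading.** Section 1.4 gives prior treatment of 12 weeks, or 24 weeks with the extension.

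- Primary baseline, entry from D3820C00005: at least about 12 × 7 = 84 days.
- Primary baseline, entry from D3820C00004 through D3820C00007: at least about 24 × 7 = 168 days.
- Either is older if a screening value is used.
- Supportive baseline: 0 days. Section 3.1.2.1 makes R1 coincide with the last treatment visit of the previous study and takes the R1 pre-dose blood pressure, pulse, ECG and Himmelsbach values from it.

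For new patients, baseline is the latest value before the first dose, normally R1 pre-dose. Section 12.2 presents data by randomized group, with new/rollover breakdowns where appropriate. A primary Week 0 table by arm would therefore combine same-morning changes in new patients with changes over about 12 to 24 weeks in rollover patients. The protocol does not state how many rollover patients are expected, so the share affected cannot be calculated.

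**The case against.** The strongest answer concerns the baseline. It would be tempting to infer that first-dose blood pressure and ECG effects in rollover patients cannot be measured under this plan. That is wrong: the supportive baseline is the same-visit pre-dose value, and Section 12.2 plans its use. Both arms also follow the same baseline rule and are randomized at R1, so drift should balance in expectation, and with no testing planned no formal decision is affected. This all stands. What remains is that the acute change is primary against the old value, supportive against the right one, and subject to the where-appropriate proviso.

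A reader might also infer that first-dose withdrawal information goes wholly unused. The protocol does not support that. The outlier analysis in Section 12.2 covers major safety variables, mentions the modified Himmelsbach scale and sets no time points, so it may take in the 2-hour score. Treatment-emergent events count from the first dose (Section 11.1.1), and events suggesting centrally mediated withdrawal are tabulated by arm (Section 12.2.1).

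A third tempting inference is that Phase II predicts withdrawal at the first dose here. Section 1.4 does report that a significantly higher total COWS "score for the NKTR-118 50 mg group was noted as compared with placebo at Day 1". That was a different scale at twice the present dose, and the difference lost significance once the GI items were removed. The eight Himmelsbach signs in Section 6.3.8 include no GI item, so the scale would not capture what drove that result. It would test, at 25 mg, the reading that central withdrawal is absent. The case for tabulating the score rests on its being a collected acute measure of a named topic, not on an expected signal.

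Finally, footnote m may be a lone wording slip, since Section 3.1.2.1 treats both arms alike in several places. That makes loss of the comparator a risk rather than a certainty.

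**Conclusion.** The point holds in three limited parts.

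- The 2-hour modified Himmelsbach score is absent from all three stated lists of summary and change-from-baseline time points: one of seven assessments after the first dose. This is not detail left to the analysis plan, because the protocol itself fixes the list three times.
- Footnote m contradicts Section 3.1.2.1 on whether Usual Care patients are scored at 2 hours. At worst, none of about 378 planned comparator scores would exist. That figure assumes full enrolment at 2:1 and every site following the footnote.
- Secondarily, the primary Week 0 blood pressure, pulse and ECG changes in rollover patients refer to values at least about 12 or 24 weeks old, while those in new patients are normally same-morning changes.

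The protocol gives no within-patient correlations, so no figure is put on the loss of precision from the older baseline, and the conclusion does not need one. The change should be made, but the study's overall conclusions do not turn on it.

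**What to change.** 1. Add Week 0 (2 hours post-dose/after initial assessments) for the modified Himmelsbach scale to Sections 6.3.1, 11.1.5 and 12.2.1. Report the observed score and the change from the R1 pre-dose score, by arm and by new versus rollover.
2. Reconcile Table 1 footnote m with Section 3.1.2.1 so that the comparator is scored at 2 hours and the between-arm summary has data in both arms.
3. For all Week 0 post-dose changes (withdrawal scale, blood pressure, pulse, ECG), name the R1 pre-dose value as the reference in every patient. For rollover patients this is already the supportive baseline. Keep the existing primary and supportive baselines for later visits.

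The cost is protocol wording and a few extra tables. Under Section 3.1.2.1 all the assessments are already scheduled, so no visit or procedure is added.

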11.1.6 Laboratory safety assessments

Changes from baseline to each visit for all patients who have a baseline laboratory test and the corresponding post-baseline laboratory test (Week 1, Week 2, Months 1, 3, 6, 9, 12, and 2 week follow-up) will be calculated as the post-baseline test value minus the baseline test value.

For the new patients, baseline laboratory values will be defined as the latest non-missing value collected prior to the first dose of study drug in this study (screening, Visit S1 or Week 0, Visit R1). For patients entering the study from a previous NKTR-118 study (D3820C00005 or D3820C00007), the primary baseline laboratory values will be defined as the latest

non-missing value collected prior to the first dose of study drug in the previous pivotal study (D3820C00004 or D3820C00005) (screening, Visit 1 or Week 0, Visit 3), and supportive baseline laboratory values will be defined as the data collected at the final visit from the previous study.

Laboratory test results will also be compared with the laboratory reference ranges, and values that are outside the applicable reference range will be flagged as high (H) or low (L). In addition, markedly abnormal values or changes from baseline will be identified.

11.1.7 Physical examination

Observed results and change from baseline to Months 6 and 12 for physical examination will be reported.

For the new patients, baseline physical examination results will be defined as the latest non-missing value collected prior to the first dose of study drug in this study (screening, Visit S1 or Week 0, Visit R1). For patients entering the study from a previous NKTR-118 study (D3820C00005 or D3820C00007), the primary baseline physical examination results will be defined as the latest non-missing value collected prior to the first dose of study drug in the previous pivotal study (D3820C00004 or D3820C00005) (screening, Visit 1 or Week 0, Visit 3), and supportive physical examination results will be defined as the data collected at the final visit from the previous study.

11.1.8 Weight

Change from baseline to Week 12 for weight will be calculated as the visit assessment minus the baseline value. Markedly abnormal values or changes from baseline will be identified.

For the new patients, baseline weight will be defined as the latest non-missing value collected prior to the first dose of study drug in this study (screening, Visit S1 or Week 0, Visit R1). For patients entering the study from a previous NKTR-118 study (D3820C00005 or D3820C00007), the primary baseline weight will be defined as the latest non-missing value collected prior to the first dose of study drug in the previous pivotal study (D3820C00004 or D3820C00005) (screening, Visit 1 or Week 0, Visit 3), and supportive baseline weight values will be defined as the data collected at the final visit from the previous study.

11.1.9 Body temperature and respiratory rate

Change from baseline to Months 6 and 12 for body temperature and respiratory rate will be calculated as the post-baseline test value minus the baseline test value. Markedly abnormal values or changes from baseline will be identified.

For the new patients, baseline temperature and respiratory rates will be defined as the latest non-missing value collected prior to the first dose of study drug in this study (screening, Visit S1 or Week 0, Visit R1). For patients entering the study from a previous NKTR-118 study (D3820C00005 or D3820C00007), the primary baseline temperature and respiratory rates will be defined as the latest non-missing value collected prior to the first dose of study drug in the previous pivotal study (D3820C00004 or D3820C00005) (screening, Visit 1 or

Week 0, Visit 3), and supportive baseline temperature and respiratory rates will be defined as the data collected at the final visit from the previous study.

